### 4.2 Secondary Outcomes

**Outcome 3:** To evaluate phylogenetic similarity of same bacterial species before and after PTD based on the core genome analysis using whole genome sequencing

- Phylogenetic analysis using whole genome sequencing of bacterial species

### 4.3 Safety Outcomes

Every PDT is documented as in routine clinics on a standardized protocol (see appendix 1).

Clinical signs and symptoms after PDT as adverse events. We will distinguish between:

- Mild redness and pain as to be expected (yes/no)
- Advanced redness and pain more than expected (yes/no): adverse event.
  - o "More than expected" is defined, if patients needs to take more than 1 painkiller/day
- Other signs and symptoms not expected (yes/no)

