#### 6.1.2 Exclusion Criteria

The presence of any one of the following exclusion criteria will lead to exclusion of the participant:

Exclusion criteria:

- Pregnant and lactating women

- Participants inability to follow the procedures of the study, e.g. due to language problems, psychological disorders, dementia, etc.,
- Participants taking antibiotics in the 14 days prior to the photodynamic treatment or until follow-up at 14 days
- Participants who received oral retinoid therapy within the last 6 months
- Participants who received anti-inflammatory agents as NSAR within the 14 days prior and after the PDT
- Participants taking any photosensitizing drugs within 4 weeks prior to the photodynamic treatment (PDT)
- Participants who had a history of photosensitivity disorder
- Fitzpatrick's skin phototype V-VI

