### **7.5 Concomitant Intervention(s)**

Since we only include participants for our analysis who do not take antibiotics or NSAR in the 14 days prior to the photodynamic treatment or until follow-up at 14 days, we will inform on that issue at the screening and at each study visit. We will record it in our eCRF.

The reason for this exclusion criteria is the impact on the bacterial skin flora and on inflammation in skin histopathology.

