### 10.3.1 Datasets to be Analyzed, Analysis Populations

All Study participants that terminated the study (n = max 20 volunteers)

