### **10.3.5 Safety Analysis**

Analysis of SAE as standard (number of adverse and serious adverse events)

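### With one analysis set and no safety set, treated volunteers whose reaction is an adverse event under 4.3 can leave the AE count, through withdrawal or through NSAR use

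*Combined protocol and SAP*

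**What the plan says.** **Adverse-event definition.** Section 4.3 has the category "Advanced redness and pain more than expected (yes/no): adverse event", and says that more than expected "is defined, if patients needs to take more than 1 painkiller/day". It names no drug class.

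**NSAR rule.** Section 6.1.2 lists "Participants who received anti-inflammatory agents as NSAR within the 14 days prior and after the PDT" among the exclusions, under the lead-in "The presence of any one of the following exclusion criteria will lead to exclusion of the participant". Section 7.5 carries this into the data: "we only include participants for our analysis who do not take antibiotics or NSAR", with a window that runs to 14 days after PDT. It gives the purpose: "The reason for this exclusion criteria is the impact on the bacterial skin flora and on inflammation in skin histopathology". NSAR use is recorded in the eCRF.

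**Withdrawal.** Section 6.3 makes withdrawal mandatory for unexpected side effects of PDT or for known ones of greater intensity. It allows five other volunteers to be asked if some are excluded, and follows those who discontinue at least once, at three weeks, for side effects. Section 8.2.4 follows volunteers withdrawn for an adverse event until it resolves and records the outcome in the CRF.

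**Analysis.** Section 10.3.1 gives one dataset for all of 10.3: "All Study participants that terminated the study (n = max 20 volunteers". Section 10.3.5 plans the "number of adverse and serious adverse events" and names no population.

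**The concern.** Both exits from the analysis happen after treatment and can be caused by it. PDT pain leads to painkillers, and if the painkiller is an NSAR the volunteer falls under 7.5. An intense reaction leads to withdrawal under 6.3, and a withdrawn volunteer is not a completer. The volunteers most likely to leave are therefore those whom the AE count exists to describe. Evaluating adverse events is a stated objective (3.4), and this pilot would supply the tolerability figure for the hip arthroplasty trial that 5.1 foresees.

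The NSAR rule also reaches back to data that the drug cannot have affected. The day-0 scraping after antisepsis is taken at the treatment visit. An NSAR taken that evening or a week later does not alter it, yet 7.5 removes the volunteer from the analysis without distinguishing time points. Section 2.4 makes sterile cultures after PDT and antisepsis the basis for planning a larger study, so these are the results the pilot most needs.

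**Working it through.** The plan states no AE rate, NSAR-use rate or withdrawal rate, so there is no figure to reproduce. The check is a reading of the rules followed by an illustration.

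**Step 1. The two routes**

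- *Withdrawal.* Reaction worse than expected (4.3), then mandatory withdrawal for more intense known side effects (6.3), then not a completer (10.3.1), then not in the 10.3.5 count if that count uses the 10.3.1 set. The painkiller plays no part. Section 6.3 gives no threshold of its own, so its overlap with 4.3 is a reading, though a natural one. PDT is given once, so withdrawal stops no further treatment. Its effect is on follow-up and analysis.
- *NSAR.* More than one painkiller a day (4.3). If the drug is an NSAR taken within 14 days after PDT, the volunteer is excluded (6.1.2) and outside the analysis (7.5). The same tablets define the event and remove it. If the drug is paracetamol, this route is closed.

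**Step 2. Effect on the AE count (assumed inputs)**

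Let n be the number treated, m the number meeting 4.3, and s the number of those m who leave by either route. The count falls from m to m − s. Without replacement, the proportion goes from m/n to (m − s)/(n − s). The number treated is itself unclear: 7.1.1 lists PDT in 20 participants, while 5.2 describes 10 control participants without PDT. Both 20 and 10 are shown.

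| n | m | s | Counted | Proportion (exact 95% CI for n = 20) |
|---|---|---|---|---|
| 20 | 4 | 0 | 4 | 4/20 = 20.0% (5.7 to 43.7) |
| 20 | 4 | 2 | 2 | 2/18 = 11.1% (1.4 to 34.7) |
| 20 | 4 | 4 | 0 | 0/16 = 0% (0 to 20.6) |
| 20 | 2 | 2 | 0 | 0/18 = 0% (0 to 18.5), against 2/20 = 10% |
| 10 | 2 | 1 | 1 | 1/9 = 11.1%, against 2/10 = 20% |
| 10 | 2 | 2 | 0 | 0/8 = 0%, against 2/10 = 20% |

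**Step 3. Chance of losing at least one case**

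Let p be the true rate of qualifying reactions and f the share of those cases that leave by either route. The probability is 1 − (1 − pf)^n.

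- p = 20%, f = 0: 0 for any n.
- p = 20%, f = 25%: 1 − 0.95^20 = 0.64 for n = 20; 1 − 0.95^10 = 0.40 for n = 10.
- p = 20%, f = 50%: 1 − 0.90^20 = 0.88 for n = 20; 1 − 0.90^10 = 0.65 for n = 10.

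**Step 4. Day-0 cultures**

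Each volunteer who takes an NSAR after PDT removes one day-0 before/after pair: 1/20 = 5% of the pairs, or 1/10 = 10% if ten are treated, without replacement. If 12 of 20 post-antisepsis cultures were sterile (60%, assumed) and four volunteers were removed, the result would lie between (12 − 4)/16 = 50% and 12/16 = 75%. The direction is unknown.

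**The case against.** A reader might infer that the plan is bound to lose adverse events through NSAR use. The documents do not support that, for four reasons.

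1. *A painkiller need not be an NSAR.* The only painkiller named is paracetamol (Appendix 1, one hour before therapy), and 7.5 has volunteers informed of the NSAR restriction at screening and at each visit. Heavy NSAR use is thus not the expected case. This stands, though nothing names a permitted painkiller after PDT, and the withdrawal route does not depend on the drug.
2. *No text ties 10.3.5 to 7.5.* The reason in 7.5 concerns skin flora and histology, so its reference to the analysis may mean only those parts. That is a reasonable reading, but nothing exempts safety, and no safety set is defined.
3. *The word terminated is ambiguous.* Section 9.4 uses it for regular and premature endings alike. On that reading withdrawn volunteers stay in the 10.3.1 set and the withdrawal route closes. Section 10.3.3 uses the word in the sense of finishing the study. The plan does not settle which applies.
4. *The data are collected.* Adverse effects are documented at the visits from PDT onward, and 6.3 and 8.2.4 continue follow-up after withdrawal (although 7.4 calls data collection and follow-up for withdrawn participants not applicable). The events could be recovered, so the loss is one of analysis only.

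Nor must the AE *proportion* be biased downwards. Removing NSAR users who had no qualifying reaction raises it: 4/20 = 20% becomes 4/18 = 22%. Replacement under 6.3 would also change the denominators. Among the volunteers originally treated, the *number* of events, which is what 10.3.5 plans, can only fall.

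**Conclusion.** The concern holds as a risk created by the written rules. Read literally, one dataset of completers, an NSAR rule without limit to particular outcomes, and mandatory withdrawal for more intense reactions allow cases meeting 4.3 to leave the AE count. The conclusion rests on reading terminated as completed (withdrawal route only) and on applying 10.3.1 and 7.5 to 10.3.5. The documents leave both open.

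The size cannot be estimated. It runs from no loss, if nobody is withdrawn or takes an NSAR, to loss of every case in the extreme. All rates in the illustration are assumptions. The day-0 culture point needs only the literal scope of 7.5 and at least one volunteer taking an NSAR after sampling.

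This is a descriptive pilot, and 2.4 rests the next step on cultures, not tolerability, so the AE part does not threaten the main result. It is still worth correcting, because these are stated rules that can select on post-treatment events and the data needed to avoid this are already collected.

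**What to change.** - **10.3.1 and 10.3.5:** define the safety set as every volunteer who received MAL or light, whatever the later NSAR use, withdrawal or replacement, and base the AE and SAE counts on it. This closes both routes.
- **7.5:** keep the day-0 cultures of all treated volunteers who had no antibiotics or NSAR before sampling. Apply the post-PDT NSAR rule only to later cultures and histopathology, where its stated reason applies.
- **7.5:** name paracetamol as the rescue painkiller after PDT. This makes NSAR use less likely but does not replace the safety set, since it leaves the withdrawal route open.

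**Cost.** No new data: NSAR use is already in the eCRF and adverse effects are already documented. The changes are to wording, but they touch the form of the analysis, so CEC approval under 1.15 is probably needed. The reported AE count may be higher than under the present rules.

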## 5 STUDY DESIGN AND COURSE OF STUDY

### 5.1 General Study Design and Justification of the Design

This is a pilotstudy of healthy volunteers, open label, and single center. If we see promising results in this pilotstudy, we will plan a prospective clinical trial in patients undergoing hip arthroplasty surgery.

[figure not shown]
The intended procedures are photodynamic treatment (PDT) on the first day followed by skin swabbing and biopsies for control of skin microbiome of treated area immediately after the PDT (outcome 1) and by controlling 3 weeks after PDT (outcome 2).

We think that this study design with healthy volunteers is adequate before starting a clinical trial.

### 5.2 Study Duration and Study Schedule

The expected duration of participant's participation is 35 days from first study visit to the last follow-up time to report side effects of photodynamic treatment. The screening visit can be any time before but at least 1 week before the first study visit. The study schedule is indicated below.

**Figure 1.** Flow chart

**Fig.1.** Study design of the PDT versus the control group

\* Only performed in 8 out of 10; \*\* only performed in 4 participants

At the day of inclusion, the voluntary participant will be informed and asked for signing the informed consent by [name] when fulfilling in- and exclusion criteria. This visit and the last visit (day 35 of the study) will be at the outpatient clinic for Infectious Diseases at the University Hospital Zurich. Demographic data (age, sex, current medications, and underlying diseases) will be noted.

Appointments for the photodynamic treatment (day 0) and the control visits (day 7 and 21) at the Department of Dermatology with Dr. [name] or at the Infectious Diseases department will be made

#### **Study schedule:**

On day 0 with [name] and [name], a skin scraping of the groin will be performed and sent for microbiological culture. Then, 5% topical methyl aminolevulinate (MAL) as the photosensitizer will be applied for 3 hours under occlusion in the right groin of the patient. After the incubation, the photodynamic process will be started by irradiation of the area with 40J/cm^2 red light from a 633nm emitting LED during 13 minutes.

Immediately after the MAL-PDT, skin antisepsis will be performed. Antisepsis of the skin is performed with a povidone-iodine/alcohol solution (Betaseptic®, Mundipharma, Limburg, Germany) and repeated three times for a total duration of 3 minutes to imitate standard surgical antisepsis before a hip arthroplasty surgery. Skin scraping will be repeated after the 3rd antisepsis and 7 and 21 days later (study visit day 7 and 21) for bacterial cultures.

As a control group, we will take skin swabs before and after skin antisepsis without PDT in 10 participants.

On day 35 ( $\pm 7$  days) of the study, volunteers will be seen for the last study visit to document any adverse effects and to inform about the individual study result.

Substudy in 5 volunteers:

In the course of the study a total of three small skin biopsies are taken (3mm diameter each) from 5 volunteers. The time and locations of the performed biopsies will be

1. from the right groin immediately after the MAL-PDT or at day 7
2. from untreated control area in the left groin after the MAL-PDT (day 0 or 7)
3. from the MAL-PDT area on day 21 as the control after treatment.

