## 4 STUDY OUTCOMES

### 4.1 Primary Outcome

**Outcome 1:** Immediate effect (Same day) of photodynamic treatment in combination with surgical antisepsis on bacterial skin colonization

- Skin swabs:
  - o Bacterial growth, density, and species before and immediately after PTD with standard bacterial cultures, MALDI-TOF for bacterial identification, semiquantitative amount of bacteria with dilution bacterial plates, molecular analysis using e.g RNA seq, whole genome sequencing
- Skin biopsies
  - o Changes of sebaceous and sweat glands after PDT (Histopathology with immunostaining)

**Outcome 2.** Long-term effect (1 and 3 weeks after PDT treatment) on bacterial skin colonization in the groin after photodynamic treatment

- Skin swabs:
  - o Bacterial growth, density, and species before and immediately after PTD with standard bacterial cultures, MALDI-TOF for bacterial identification, semiquantitative amount of bacteria with dilution bacterial plates, molecular analysis using e.g RNA seq, whole genome sequencing
- Skin biopsies
  - o Changes of sebaceous and sweat glands after PDT (Histopathology with immunostaining)

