## 7.2 Administration of Study Intervention

### 7.2.1 Study Intervention

Details of study Intervention	Justification
1. Inguinal skin scraping before photodynamic treatment	Baseline microbiome data
2. Natural bacterial porphyrin fluorescence photography	Baseline fluorescence photography
3. Photosensitizer application, followed by fluorescence photography Photodynamic therapy (PHT) (1x) over 15 minutes at the dermatology ward	Treatment to kill bacteria and to reduce glands in order to reduce colonization bacteria
4. Skin antisepsis in the groin, skin scraping after antisepsis	To measure bacterial colonization to know the immediate effect of PDT
5. Punch biopsy  specimen of the MAL-PDT area (immediately after PDT) and of an untreated area as a control	To analyze size and structure of glands in the skin
6. Inguinal skin scraping and punch biopsy of the MAL-PDT area after 7 and 21 days	To measure bacterial colonization to know the long-term effect of PDT

 only in 5 participants

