## Skin Biopsies

This will be done by the dermatologist Dr. med. [name] in 5 volunteers. A small piece of skin (3 mm) will be taken and transferred to a sterile tube for microbiological culture and histopathology. The skin biopsies will be taken after a local anesthesia. The wound will be closed with one stitch.

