**Study schedule:**

Substudy in 5 volunteers:

In the course of the study a total of three small skin biopsies are taken (3mm diameter each) from 5 volunteers. The time and locations of the performed biopsies will be

1. from the right groin immediately after the MAL-PDT or at day 7
2. from untreated control area in the left groin after the MAL-PDT(day 0 or 7)
3. from the MAL-PDT area on day 21 as the control after treatment.

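### The protocol caps the substudy at three punch biopsies per volunteer in sections 5.2 and 8.3.1, but the 7.2.1 table lists four

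*Combined protocol and SAP*

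**What the plan says.** Section 5.2 (Study schedule, substudy) says that "a total of three small skin biopsies are taken (3mm diameter each) from 5 volunteers". It then lists them. The first is taken "from the right groin immediately after the MAL-PDT or at day 7"; the second comes from the untreated left groin, on day 0 or day 7; the third comes from the treated area on day 21. Section 8.3.1 repeats the same total and the same list.

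The table in section 7.2.1 covers the same procedures differently. Row 5 is a punch biopsy "specimen of the MAL-PDT area (immediately after PDT) and of an untreated area as a control". Row 6 reads "Inguinal skin scraping and punch biopsy of the MAL-PDT area after 7 and 21 days". The table states no total and does not offer day 0 and day 7 as alternatives. Its only footnote restricts biopsies to five participants.

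Section 8 (Skin Biopsies) describes what each one involves: "The skin biopsies will be taken after a local anesthesia. The wound will be closed with one stitch".

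**The concern.** The number of invasive samples per person is an operating instruction, and the protocol gives two. Staff working from 7.2.1, which is the table that sets out the intervention in detail, would take one biopsy more per healthy volunteer than the total in 5.2 and 8.3.1. Each extra biopsy means another local anaesthetic and another stitch. Section 1.8 names biopsies in its minimal-risk classification, and section 8.2.1 (Histopathology) requires a separate substudy consent, so the number should be unambiguous.

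The gland data are affected too. Section 4.1 lists gland changes under the same-day outcome and again under the 1- and 3-week outcome. With the three biopsies of 5.2, a volunteer gives a same-day or a 1-week treated sample, never both, and no rule says who is sampled on which day.

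**Working it through.** This is a direct count; no power or sample-size formula applies.

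**Inputs.** The biopsy lists in 5.2 and 8.3.1, rows 5 and 6 of the 7.2.1 table, and five substudy volunteers (5.2, 7.1.1, 7.2.1).

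**Count per volunteer**

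| Specimen | 5.2 and 8.3.1 | 7.2.1 |
|---|---|---|
| Treated, day 0 | 1 in total for day 0 or day 7 | 1 (row 5) |
| Treated, day 7 | (included above) | 1 (row 6) |
| Untreated control | 1 | 1 (row 5) |
| Treated, day 21 | 1 | 1 (row 6) |
| **Total** | **3** | **4** |

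1. Stated total: 1 + 1 + 1 = 3. The list in 5.2 and 8.3.1 reproduces its own figure.
2. Table 7.2.1: 2 (row 5) + 2 (row 6) = 4.
3. Difference: 4 − 3 = 1 per volunteer; 1/3 = 33%.
4. Across five volunteers: 3 × 5 = 15 against 4 × 5 = 20, a difference of 5.

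The whole difference comes from the early treated sample: day 0 or day 7 in 5.2, day 0 and day 7 in 7.2.1.

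**Does another section settle it?**

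- *Visit lists, 8.3.2 to 8.3.4.* Each of days 0, 7 and 21 has a line for punch biopsies in five participants, without a number per person. That fits four. It also fits three, for example treated on day 0, untreated on day 7, treated on day 21.
- *Schedule, 8.1.* The row for treated plus untreated specimens is ticked on days 0 and 21, and the treated-area row on days 7 and 21. Read literally, the distinct specimens are treated on days 0, 7 and 21 and untreated on days 0 and 21: 3 + 2 = 5. This widens the conflict.
- *Section 8.2.1.* Histopathology is placed at visit 2 (day 0) and at a visit 3 described as 21 days. In 8.3.3 and 8.3.4, visit 3 is day 7 and visit 4 is day 21, so the label no longer matches the visits.

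**Effect on the early gland data.** Under 5.2, n(day 0) + n(day 7) = 5. The possible splits, in either direction, are 5/0, 4/1 and 3/2. If both days are used, the smaller group is 1 or 2 volunteers. Under 7.2.1 it is 5 on each day.

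**The case against.** The best defence is that the protocol already favours three. Sections 5.2 and 8.3.1 are the only places that state a total, and they agree. Row 6 of 7.2.1 combines scraping with biopsy, and scraping does take place on both days, so the row could be a list of possible time points. Section 8.2.1 names no day-7 histology, and section 5.1 describes biopsies right after PDT and a control at three weeks; both fit a plan of three. One dermatologist takes all the biopsies under separate consent, the analysis is meant to be descriptive, and every volunteer still gives a day-21 treated sample.

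Some of this stands. Three is the likelier intention, no efficacy conclusion turns on the count, and a 5/0 split is allowed under 5.2. But the time-point reading is not in the table, so a reader would have to bring the limit in from another section. The 8.1 schedule points away from three.

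A fair caution concerns the totals. The Figure 1 legend in 5.2 says that one item is done in only four participants, and the figure is not available to show which. If that item is the biopsies, the totals become 3 × 4 = 12 against 4 × 4 = 16. The difference of one per volunteer is unchanged.

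**Conclusion.** The point holds: the protocol is wrong as written. Two sections fix three biopsies per volunteer and the intervention table lists four, an excess of one (33%), or 15 against 20 in the substudy. This rests on reading the stated total as per volunteer, which the list of sites and days within one person supports, and on five substudy volunteers. The consent text was not available, so nothing is claimed about whether four would exceed it.

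The practical weight is moderate: one additional 3 mm biopsy per healthy volunteer, and an early gland comparison that may be split between two days. The count conflict is certain from the text; the split arises only if both early days are used.

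**What to change.** 1. Reword rows 5 and 6 of 7.2.1 and the biopsy rows of 8.1 to give the 5.2 list: treated area on day 0 or day 7 but not both, untreated left groin once, treated area on day 21. In 8.1, remove the tick that implies a second untreated biopsy on day 21.
2. Preferably set one early day for all five volunteers, and state in 4.1 which gland time points the biopsies then cover. Sections 5.1 and 8.2.1 already lean towards day 0. If the choice stays open, repeat the either/or condition in the visit 2 and visit 3 lists.
3. Correct the visit label in 8.2.1 so that day 21 is visit 4.
4. If the investigators do intend four, change the total and list in 5.2 and 8.3.1 instead, and check the number against the substudy consent.

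Items 1 to 3 cost protocol wording only. Item 4 adds the consent check.

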### 5.3 Methods of Minimizing Bias

Excluded bias in our collective

- No selected participants
- Both sex can be included
- Any age

Potential bias in our collective:

- Since we will search for healthy volunteers, the microbiome analysis might be slightly different to the population undergoing a hip arthroplasty surgery in an orthopedic hospital.

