## Photodynamic treatment

This will be done by the dermatologist Dr. med. [name]. She will apply 5% topical methyl aminolevulinate (MAL) as the photosensitizer for 3 hours under occlusion in the right groin of the participant. She will then start the photodynamic process by irradiation of the area with 40J/cm^2 red light from a 633 nm emitting LED during 13 minutes.

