**8.3.2 Visit 2 = Day 1 of the study**

On day 1 with [name] and [name], a skin scraping of the groin will be performed and sent for microbiological culture. Then, 5% topical methyl aminolevulinate (MAL) as the photosensitizer will be applied for 3 hours under occlusion in the right groin of the patient. After the incubation, the photodynamic process will be started by irradiation of the area with 40J/cm^2 red light from a 633nm emitting LED during 13 minutes.

Immediately after the MAL-PDT, skin antisepsis will be performed. Antisepsis of the skin is performed with a povidone-iodine/alcohol solution (Betaseptic®, Mundipharma, Limburg, Germany) and repeated three times for a total duration of 3 minutes to imitate standard surgical antisepsis before a hip arthroplasty surgery.

For all inguinal swabs, we will use the scratching method using a scalpel as already applied in a previous study (ethical approval BASEC-Nr 2016-01017). The swabs will be sent to the microbiology laboratory of the University of Zurich for bacterial analysis (analysis under supervision of Prof. [name]).

Skin biopsies will be done as a routine procedure at the Department of dermatology.

In short:

- Inguinal skin scraping before PDT
- Natural bacterial porphyrin fluorescence photography
- Study intervention: Photosensitizer application for 3 hours
- PDT for 15 minutes
- Inguinal skin scraping
- Skin antisepsis with povidone/iodine (3x times for 1 minute)
- Inguinal skin scraping
- Punch biopsies in 5 participants
- Documentation of adverse effects

Duration: 4 hours

Location: Department of dermatology, University Hospital Zurich

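### In the five-volunteer biopsy substudy PDT is always on the right and the untreated biopsy always from the left, so the gland contrast cannot be separated from side

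*Combined protocol and SAP*

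**What the plan says.** Three descriptions of the procedure fix the treated side. Section 5.2 (Study schedule) applies the photosensitiser "for 3 hours under occlusion in the right groin of the patient". Section 8.1 (Photodynamic treatment) has "for 3 hours under occlusion in the right groin of the participant", and section 8.3.2 agrees: "will be applied for 3 hours under occlusion in the right groin of the patient". None gives a reason for choosing that side.

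For the substudy, section 5.2 states that "a total of three small skin biopsies are taken (3mm diameter each) from 5 volunteers". The first specimen comes "from the right groin immediately after the MAL-PDT or at day 7", the second "from untreated control area in the left groin after the MAL-PDT (day 0 or 7", and the third "from the MAL-PDT area on day 21 as the control after treatment". The same list is repeated after section 8.3.1. The tables in 7.2.1 and 8.1 speak only of an untreated area, which is compatible. No specimen is listed before treatment.

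Section 4.1 places gland change under both parts of the primary outcome, and 8.2.1 lists histopathology as a primary assessment. The study plan table in 8.1 labels the biopsy with untreated control as a secondary measure. Section 5.3 on minimising bias lists features of the participants, for example "Both sex can be included". It mentions neither side nor the reading of specimens. The study is open label (section 5.1).

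**The concern.** Half of the hypothesis in section 10.1 is that PDT destroys sebaceous and sweat glands. Within the study, the only untreated tissue against which that can be judged is the left-groin biopsy. The day 21 specimen does not help: it comes from treated skin, so comparing it with the early right-groin specimen follows change over time after PDT but supplies no untreated reference.

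Because all five pairs have the same orientation, any systematic difference between the two groins, or between how the two sides are sampled, would be read as a PDT effect. A descriptive analysis offers no protection, since the bias sits in the estimate itself.

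The second consequence concerns assessment. The histology in 8.2.1 looks for shrinkage, destruction or marked atrophy of gland lobules, which involves judgement. With side fixed, a reader who sees right or left on an early specimen knows whether it was treated.

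**Working it through.** The plan has no figure of its own to reproduce here. The target of 20 in section 10.2 comes without an effect size, SD or power, and this point does not depend on it.

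**Inputs.** Five volunteers with one treated-untreated pair each (section 5.2); treated side right in all five (5.2, 8.1, 8.3.2); untreated side left in all five (5.2). The systematic right-minus-left difference d is not in the documents and is treated as an assumption.

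**Step 1: can treatment and side be separated?** Write each observation as person + treatment + side. For five pairs this is 5 + 1 + 1 = 7 columns. As planned, treatment is present exactly when the side is right, so two columns coincide and the rank is 6 of 7. No analysis can recover the missing term. With both orientations present the rank is 7 of 7.

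**Step 2: bias of the mean treated-minus-untreated difference.** If k of n volunteers are treated on the right, each of these contributes +d and each of the other n − k contributes −d:

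bias = d(2k − n)/n

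- k = 5, n = 5 (as planned): d(10 − 5)/5 = d
- k = 3, n = 5: d(6 − 5)/5 = d/5
- k = 2, n = 5: d(4 − 5)/5 = −d/5

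If chance also decides which side receives three volunteers, the expected bias is 0.

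A 3:2 split further allows adjustment for side. Right-treated pairs have mean effect + d and left-treated pairs effect − d, so the simple average of the two means removes d. Its variance is (1/4)(1/3 + 1/2) = 0.208, against 1/5 = 0.200, in units of the squared SD of the within-person difference.

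**Step 3: mean squared error over an assumed range.** Let s be d in SDs of the within-person difference. MSE = 1/5 + bias²:

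| s (assumed) | Fixed side: 0.2 + s² | Simple random side: 0.2 + s²/5 | 3:2 split: 0.2 + s²/25 |
|---|---|---|---|
| 0 | 0.20 | 0.20 | 0.20 |
| 0.25 | 0.26 | 0.21 | 0.20 |
| 0.5 | 0.45 | 0.25 | 0.21 |
| 1.0 | 1.20 | 0.40 | 0.24 |

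Randomising the side never raises the MSE. When s = 0, nothing is lost.

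**Step 4: why a restricted list.** Independent coin tosses put all five volunteers on one side with probability 2 × (1/2)^5 = 0.0625, which would restore the aliasing. A 3:2 list excludes this.

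**Sensitivity to the number of pairs.** A footnote to the flow chart in 5.2 mentions four participants, but the figure is not shown, so what the footnote marks is uncertain. If it were the biopsies, fixed side still gives bias d, and a 2:2 split gives d(4 − 4)/4 = 0.

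**The case against.** The strongest objection concerns scope. A reader might infer that the trial's whole treated-versus-untreated comparison is confounded with side. The documents do not support that. The primary analysis in 10.3.2 compares microbiological data before and after PDT, and no left-groin scraping is described in treated volunteers. No side is stated for the 10 participants swabbed without PDT, so confounding by side is not shown there either. This part of the objection stands, and the point is confined to the biopsies.

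It can also be said that nothing in the documents suggests the two groins differ in gland number or size. That too stands: the aliasing is proven, a material bias is not. It does not remove the point, because the planned data could never show whether d is small.

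A reader might say that masked reading fails. The study is open label and describes no masked histology, so there is nothing planned to fail. Coded labels would also hide treatment with side fixed, and randomising the side masks nobody without coding. What remains is that a visible side label discloses treatment on an early specimen.

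Finally, randomising the side might be called free. It is free in participants and procedures only. The treated side must be followed across visits that may take place in either of two departments (8.3.3, 8.3.4).

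**Conclusion.** The point holds for the biopsy substudy. The treated-untreated gland contrast is completely aliased with side in all five pairs, and no later analysis can undo this. Any systematic side difference d enters in full. A 3:2 split would cut it to one fifth, with expectation 0 if the orientation is drawn at random. These results assume that d adds to the treatment effect and is the same for all volunteers. The documents give no value for d, so nothing can be said about how large the bias is.

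This is a cheap improvement to a small descriptive substudy, not a flaw in the swab comparison. Gland change appears under the primary outcome in 4.1, although the 8.1 table calls the biopsy secondary; under either label, this pair is the only untreated tissue reference within the study.

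Side allocation would not settle a separate matter in the same list. Both early specimens may be taken on day 0 or day 7 with no rule that they share a day, so a time difference can remain.

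**What to change.** In sections 5.2, 8.1 and 8.3, replace right groin and left groin by treated groin and untreated groin. For substudy volunteers, assign the treated side from a list prepared in advance with a 3:2 split, and let chance decide both the order and which side receives three. Record the side in the eCRF. Label histology specimens with a code that shows neither side nor treatment.

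Cost: no added visit, biopsy or participant. The treated side must be checked at the day 7 and day 21 visits. Substudy consent, which is separate and optional, must be known before the side is assigned. Five cannot be split evenly, so d/5 remains unless the summary adjusts for side. As a change of design, this needs ethics committee approval under section 1.15. Version v04 is dated January 2020 and the first participant was planned for July 2019, so the change may reach only the remaining volunteers. If four have already been treated on the right, the best reachable bias is d(8 − 5)/5 = 3d/5.

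If the side stays fixed, say in 5.3 that the biopsy contrast is confounded with side, and report it with that qualification.
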